2.3 Treatment Assignment and Blinding

FC participants (LIN-MD-62 and LIN-MD-64 completers) will receive open-label linaclotide 72 μ g or 145 μ g once daily for 24 weeks as follows based on their age at the time of enrollment into LIN-MD-66:

- 6 to 11 years of age: 72 μ g linaclotide
- 12 to 17 years of age: will be randomly assigned at 1:1 ratio to 72 μ g linaclotide or 145 μ g linaclotide

IBS-C participants will receive linaclotide for 52 weeks as follows:

- LIN-MD-63 completers will receive open-label linaclotide 290 µg once daily except for the LIN-MD-63 completers who had received \leq 145 µg linaclotide or placebo. These participants will have the option to receive open-label linaclotide 145 µg once daily.
- LIN-MD-64 completers will have the option to either remain on the same blinded linaclotide dose they were receiving during the lead-in study LIN-MD-64 or receive open-label 290 µg linaclotide.
 - LIN-MD-64 completers who choose to remain on the same blinded linaclotide dose received during the lead-in study LIN-MD-64 will continue to receive blinded linaclotide 145 or 290 µg once daily.
 - LIN-MD-64 completers who choose to receive open-label linaclotide therapy will receive linaclotide 290 µg once daily.

Participants who experience an intolerable AE that may be related to the use of linaclotide can be dose reduced one dose level only during the course of the study at the investigator's discretion as shown in [Table 1](#). Subsequent dose adjustments (between the initial dose and reduced dose) are also permitted at the investigator's discretion. Participants receiving blinded linaclotide treatment will be dose adjusted in a blinded fashion via IWRS.

The decision of whether to temporarily suspend dosing or dose reduce following the occurrence of an intolerable AE is per the investigator's discretion.

Table 1. Dose Reductions

	IBS-C				FC	
	Open-label (µg)		Blinded (µg)		Open-label (µg)	
Initial dose	290	145	290	145	145	72
Reduced dose	145	72	145	72	72	N/A

2.4 Sample Size Determination

At least 120 participants are planned to be enrolled in this long-term safety study. However, the actual number of participants in this study will depend on the number of participants who complete the lead-in studies (LIN-MD-62, LIN-MD-63, and LIN-MD-64) and who are eligible to be enrolled into this long-term study after fulfilling the eligibility criteria. The sample size in this study is not driven by any statistical consideration.

3.0 Endpoints

3.1 Efficacy Endpoint

There is one other efficacy endpoint in this study:

- The achievement of no longer fulfilling Rome III criteria at the end of study intervention period

3.2 Safety Endpoints

The safety parameters will include:

- adverse events (AEs)
- clinical laboratory parameters
- vital signs
- electrocardiograms (ECGs)
- height
- weight

4.0 Analysis Populations

For this long-term safety study, only 1 analysis population, i.e., Safety Population, is considered. The Safety Population is defined as all enrolled participants who received at least one dose of study intervention in this study. Participants will be summarized according to the study intervention they actually received.

If a participant received study intervention other than the original assigned study intervention, actual study intervention received will be determined based on the study intervention received for the majority of the study intervention period. If there is a tie, the higher dose will be considered the actual study intervention for that participant. This is also relevant for participants who require dose de-escalation/escalation in this long-term safety study.

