6.6. Dose Modification

At the discretion of the investigator, any participant who experiences an AE intolerable enough to prompt a consideration of study withdrawal may receive a temporary suspension of dosing. The duration of a dosing suspension will be at the investigator's discretion; however, after a participant has been off study intervention for 3 days, or if the participant requires a suspension of dosing on more than 1 occasion, the investigator must contact the sponsor to discuss the participant's continued participation in the study.

Participants who experience an intolerable AE that may be related to the use of linaclotide can be dose reduced one dose level only during the course of the study at the investigator's discretion as shown in [Table 6-1](#). Subsequent dose adjustments (between the initial dose and reduced dose) are also permitted at the investigator's discretion. Participants receiving blinded linaclotide treatment will be dose adjusted in a blinded fashion via IWRS.

Table 6-1 Dose Reductions

	IBS-C				FC	
	Open-label (µg)		Blinded (µg)		Open-label (µg)	
Initial dose	290	145	290	145	145	72
Reduced dose	145	72	145	72	72	N/A

The decision of whether to temporarily suspend dosing or dose reduce following the occurrence of an intolerable AE is per the investigator's discretion.

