9.0 Safety Analyses

9.1 General Considerations

All safety analyses or summaries will be performed by study intervention group using the safety population, for overall and for each age group (6 to 11 years and 12 to 18 years in FC; 7 to 11 years and 12 to 18 years in IBS-C) separately for FC and IBS-C participants.

For each safety parameter (laboratory, vital signs, body weight, height, and ECG), the baseline will be defined as below:

- If participants enroll into LIN-MD-66 within 28 days of last dose date of the lead-in study, baseline of the lead-in study will be used as the baseline value in LIN-MD-66.
- If participants enroll into LIN-MD-66 after 28 days of last dose date of the lead-in study, the last non-missing assessment made before the first dose of the study intervention in this study will be used as the baseline value in LIN-MD-66.

Safety data analyses will be provided descriptively based on the observed safety data, without data imputation for missing safety parameters.

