9.2.1 Treatment-Emergent Adverse Events

An AE will be considered a treatment emergent adverse event (TEAE) if:

- The AE began on or after the date of the first dose of study intervention in LIN-MD-66; or
- The AE was present before the date of the first dose of study intervention in LIN-MD-66 but increased in severity or became serious on or after the date of the first dose of study intervention in LIN-MD-66.

However, an AE that occurs more than 30 days after the last dose of study intervention in LIN-MD-66 will not be counted as a TEAE.

An AE will be considered a treatment emergent serious adverse event (TESAE) if it is a TEAE that additionally meets any serious adverse event (SAE) criterion.

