9.2.3 Treatment-Emergent Adverse Events by SOC and/or PT

The number and percentage of participants reporting TEAEs will be tabulated by SOC and preferred term; and by SOC, preferred term, and severity.

The number and percentage of participants reporting treatment-related TEAEs will be tabulated by SOC and preferred term.

If more than one event is coded to the same preferred term for the same participant, the participant will be counted only once for that preferred term using the greatest severity for the summarization by severity.

If the severity of a TEAE is missing, the maximum severity will be assigned to the event for the summarization by severity. The value will be displayed as missing in the data listing.

If the relationship to the study intervention is missing for a TEAE, the event will be considered related to the study intervention for the summarization. The value will be displayed as missing in the data listing.

Listings of all the AEs will be presented.

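### SAP 4.0 labels participants by majority dose even after a reduction prompted by an AE, so AE tables can show events that began on the higher dose under the lower dose

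*SAP*

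**What the plan says.** SAP 4.0 defines the treatment group for anyone who received something other than the original assignment: "actual study intervention received will be determined based on the study intervention received for the majority of the study intervention period". It adds "If there is a tie, the higher dose will be considered the actual study intervention for that participant" and then "This is also relevant for participants who require dose de-escalation/escalation in this long-term safety study".

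The trigger for de-escalation is in SAP 2.3 and Protocol 6.6: "Participants who experience an intolerable AE that may be related to the use of linaclotide can be dose reduced one dose level only". The permitted steps (SAP Table 1, Protocol Table 6-1) are 290 to 145 µg and 145 to 72 µg in IBS-C, and 145 to 72 µg in FC. FC participants who start on 72 µg have no lower level. Protocol 6.6 continues: "Subsequent dose adjustments (between the initial dose and reduced dose) are also permitted".

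SAP 9.1 carries the label into every safety table: "All safety analyses or summaries will be performed by study intervention group using the safety population". SAP 9.2.3 states "The number and percentage of participants reporting TEAEs will be tabulated by SOC and preferred term". SAP 9.2.4 computes the exposure-adjusted incidence rate (EAIR) with time at risk running from first dose to first onset, or over the whole treatment duration if there is no event. SAP 9.2.7 adds the diarrhea summaries. None of these sections assigns an AE to the dose taken at onset, divides time at risk by dose, or tabulates by initial dose.

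**The concern.** A majority-dose label suits dispensing errors, where the departure from assignment has nothing to do with outcome. Here the change of dose is a response to an AE, so the column in which an AE appears can depend on that AE.

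The by-dose AE columns are at stake. They include the columns for the only randomised allocation in the study (FC aged 12 to 17, 72 vs 145 µg, Protocol 6.3). In FC, permitted dose adjustments can move a label only from 145 to 72 µg. In IBS-C, participants reduced early from 145 µg would form a 72 µg group that is not among the planned arms in Protocol 10.6 and would contain only participants reduced for an intolerable AE.

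**Working it through.** The plan has no figure to reproduce: SAP 2.4 says the sample size has no statistical basis, and SAP 11.0 plans no testing. The check applies the rules as written.

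**1. Switch point.** Take full-length treatment and one sustained reduction.
- FC: 24 × 7 = 168 days, half is 84. A participant with 83 days on 145 µg and 85 on 72 µg is labelled 72 µg. At 84 vs 84 the tie rule gives 145 µg.
- IBS-C: 52 × 7 = 364 days, half is 182. A participant with 181 days on the initial dose and 183 on the reduced dose takes the reduced-dose label. At 182 vs 182 the higher dose is kept.
- The diarrhea onset categories in SAP 9.2.7 up to Week 11 end at day 11 × 7 = 77, before the FC switch point. A prompt, sustained reduction after onset in those categories would usually change the label.

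The SAP does not say whether the period is planned or actual for early stoppers, so these cut-offs are for full-length participants.

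**2. Direction.** An early sustained reduction puts the prompting AE under the lower dose. In the EAIR for that event, the time at risk placed there is time on the higher dose. After a late reduction or an exact tie, the higher label stays, and an AE that first begins on the lower dose is counted under the higher dose. A participant who stops before any reduction is not moved. Re-escalation is permitted, so the label depends on the whole dose history.

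**3. Size, FC aged 12 to 18, equal arms (all risks assumed).** Let m be the share of the 145 µg arm who are cases of a given AE and are relabelled after early reduction; p145 and p72 are the true risks.

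- Tabulated 145 µg = (p145 − m)/(1 − m)
- Tabulated 72 µg = (p72 + m)/(1 + m)
- Columns equal at m = (p145 − p72)/(2 − p145 − p72)
- EAIR, onset at day 14: 145 µg = 36525 × (p145 − m)/[168(1 − p145) + 14(p145 − m)]; 72 µg = 36525 × (p72 + m)/[168(1 − p72) + 14(p72 + m)]

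At m = 2% with 15% vs 8%: 0.13/0.98 = 13.3% and 0.10/1.02 = 9.8%.

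| True risks | m | 145 µg vs 72 µg | Gap (points) | EAIR per 100 patient-years |
|---|---|---|---|---|
| 15% vs 8% | 0 | 15.0% vs 8.0% | 7.0 | 37.8 vs 18.8 |
| 15% vs 8% | 0.9% | 14.2% vs 8.9% | 5.3 | 35.5 vs 20.9 |
| 15% vs 8% | 2% | 13.3% vs 9.8% | 3.5 | 32.8 vs 23.4 |
| 10% vs 5% | 0 | 10.0% vs 5.0% | 5.0 | 23.9 vs 11.4 |
| 10% vs 5% | 0.9% | 9.2% vs 5.9% | 3.3 | 21.7 vs 13.5 |
| 10% vs 5% | 2% | 8.2% vs 6.9% | 1.3 | 19.2 vs 15.9 |

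The columns become equal at 0.07/1.77 = 3.95% and at 0.05/1.85 = 2.70%.

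**4. What m might be.** The only proxy is discontinuation for diarrhea on linaclotide in the two Phase 2 studies (Protocol 2.2.2): one in each, 2/214 = 0.93%, exact 95% interval 0.1% to 3.3%. It covers 4 weeks, counts discontinuation rather than reduction, and comes mostly from lower doses. The 0.9% rows use it.

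**5. In participants.** With 50 per arm (assumed), 0.93% is 0.47 participants on average, and the chance that nobody moves is (1 − 2/214)^50 = 62.5%. A 2% shift is one participant. By exact binomial enumeration at 15% vs 8%, the chance that the 145 µg column is strictly higher is 83.0% with none moved, 78.3% at 0.9% and 70.2% at 2%.

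No figure is given for IBS-C. LIN-MD-64 completers choose their treatment there, and group sizes are unknown.

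**The case against.** The majority rule is explicit, pre-specified and has a tie-break. It is compatible with Protocol 9.3, which calls for summaries by the intervention actually received. No single label is clean: grouping by initial dose would include AEs that first begin after reduction. The objective (SAP 2.1) is long-term safety, not comparison of doses. There are no hypotheses or tests, totals pooled over doses do not change, and all AEs are listed. Table specifications are in a separate document (SAP 1.0) that is not available here. At the proxy rate, fewer than one participant in 50 is expected to move.

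All of this stands, and it limits the weight of the point. It does not remove the mechanism, because a listing does not correct a column percentage and the SAP itself requires no display by dose at onset.

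A reader might infer that the tables would reverse the dose ordering. The documents do not support that. For example, with 30 per dose and 6 vs 2 events (assumed), relabelling 3 of the 6 gives 3/27 = 11.1% vs 5/33 = 15.2%. That needs 3 of 30, or 10%, of the arm to move, well above the proxy's upper limit of 3.3%. A reader might also infer that the SAP contradicts Protocol 9.3. It does not: both the majority dose and the initial dose were actually received.

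**Conclusion.** The point holds as a matter of how the SAP would be executed. Early reductions can place the prompting AE and its time at risk under the reduced dose, and late reductions can place new AEs under the higher dose. In FC, dose adjustment moves labels only from 145 to 72 µg.

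The size is unknown. Under the assumed risks, one moved case in 50 halves a 7.0-point gap to 3.5 points; at the proxy rate the gap shrinks to 5.3 points and the order is kept. Reversal at 15% vs 8% needs more than 3.95%, above the proxy interval. At 10% vs 5% it needs more than 2.70%, which lies inside that imprecise interval, so it is neither shown nor excluded. The late-reduction effect is not quantified. It concerns mainly other preferred terms, because a participant already counted for the prompting term is not counted again.

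This should be fixed, at low priority. It affects the by-dose reading of a descriptive safety study, not its pooled conclusions.

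**What to change.** Change the analysis only; no dosing rule is involved.

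- In SAP 4.0, for dose adjustments the protocol permits, group all AE outputs by the initial dose taken in LIN-MD-66: overview, TEAE, EAIR, TESAE, discontinuation, AESI and diarrhea tables, and the displays of AEs in participants with PCS values. Use matching denominators and show exposure Ns by initial dose.
- Add one supportive TEAE/EAIR table by dose taken at AE onset, with time at risk split at each dose change. Assign AEs that start during a suspension or after the last dose to the last dose taken, within the SAP 9.2.1 window, which excludes "an AE that occurs more than 30 days after the last dose of study intervention". Show IBS-C 72 µg there only as person-time, not as a group.
- Report the number and timing of reductions and re-escalations by initial dose.
- Keep the majority rule for dispensing errors. State which label the laboratory, ECG, height, vital-sign and weight tables use, and footnote any difference in column Ns.

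The cost is one exception in SAP 4.0, one supportive table and one count. Dose dates are already needed to apply the majority rule, so no new data are required. The downside is that initial-dose columns will include AEs of other preferred terms that first begin after reduction; the dose-at-onset table shows these.

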5.0 Subject Disposition

Number of participants screened for the study will be provided.

The summary of study disposition during study intervention period will be provided by study intervention group for overall and for each age group (6 to 11 years and 12 to 18 years in FC; 7 to 11 years and 12 to 18 years in IBS-C) separately for FC and IBS-C participants for the following:

- Number of participants enrolled (at Visit 2/Day 1) (Note: This frequency count will be used as the denominator to calculate the percentages described below)
- Number and percentage of participants received placebo in the Lead-in Study
- Number and percentage of participants treated
- Number and percentage of participants completed the study drug
- Number and percentage of participants prematurely discontinued study drug (all reasons)

6.0 Study Drug Duration and Compliance

For the safety population, duration of treatment will be summarized for each study intervention group overall and for each age group (6 to 11 years and 12 to 18 years in FC and 7 to 11 years and 12 to 18 years in IBS-C) separately for FC and IBS-C participants. Duration of treatment is defined for each participant as last dose date minus first dose date + 1 in this study. Duration of treatment will be summarized using the number of participants treated, mean, standard deviation, median, minimum and maximum. In addition, the number and percentage of participants in each treatment duration category (defined below) will be summarized.

- FC participants: ≤ 4 weeks, $> 4 - \leq 8$ weeks, $> 8 - \leq 12$ weeks, $> 12 - \leq 18$ weeks, $> 18 - \leq 24$ weeks, > 24 weeks
- IBS-C participants: ≤ 4 weeks, $> 4 - \leq 8$ weeks, $> 8 - \leq 12$ weeks, $> 12 - \leq 20$ weeks, $> 20 - \leq 28$ weeks, $> 28 - \leq 36$ weeks, $> 36 - \leq 44$ weeks, $> 44 - \leq 52$ weeks, > 52 weeks

Additionally, total continuous exposure with any linaclotide doses across the lead-in studies and Study LIN-MD-66 will also be summarized. Participants who received linaclotide, completed the lead-in study, and enrolled in Study LIN-MD-66 within 28 days from last study intervention will be considered to have continuous exposure. The continuous exposure of linaclotide will be calculated as the sum of the exposure from the lead-in study and from Study LIN-MD-66. The number and percentage of participants in each treatment duration category (defined below) will be summarized.

- FC participants: ≥ 4 weeks, ≥ 12 weeks, ≥ 24 weeks, ≥ 30 weeks, ≥ 36 weeks
- IBS-C participants: ≥ 4 weeks, ≥ 12 weeks, ≥ 24 weeks, ≥ 36 weeks, ≥ 48 weeks, ≥ 52 weeks, ≥ 64 weeks

Treatment compliance is defined as the number of capsules actually taken by a participant divided by the number of capsules expected for the same period multiplied by 100. The information period will be based on the information from 'Exposure Form' of the participant's electronic case report form (eCRF). The number of capsules expected to be

taken in a specific treatment period will be calculated by multiplying the number of days in that period by the number of capsules to be taken per day.

Descriptive statistics for study drug compliance will be presented by study intervention group using the safety population, for overall and for each age group (6 to 11 years and 12 to 18 years in FC; 7 to 11 years and 12 to 18 years in IBS-C) separately for FC and IBS-C participants.

7.0 Demographics, Baseline Characteristics, Medical History, and Prior/Concomitant Medications

Demographics, baseline characteristics, medical history, and prior and concomitant medications will be summarized for the safety population by study intervention group, for overall and for each age group (6 to 11 years and 12 to 18 years in FC; 7 to 11 years and 12 to 18 years in IBS-C) separately for FC and IBS-C participants. Categorical variables will be summarized with the number and percentage of participants; percentages will be calculated based on the number of non-missing observations. Continuous variables will be summarized with descriptive statistics (number of non-missing observations, mean and standard deviation, median, minimum and maximum).

7.1 Demographics and Baseline Characteristics

Demographic variables include:

- Age (based on informed consent date)
- Age group (6 to 11 years and 12 to 18 years in FC; 7 to 11 years and 12 to 18 years in IBS-C)
- Sex (Male, Female)
- Race (White, Black or African American, Asian, American Indian or Alaska Native, Native Hawaiian or Other Pacific Islander, Other)
- Ethnicity (Hispanic or Latino, not Hispanic or Latino)

Baseline characteristics variables include:

- Weight (kg)
- Height (cm)
- Body mass index (calculated as weight [kg]/ height[m]²)

The baseline is defined as the baseline of the lead-in study if participants enroll into LIN-MD-66 within 28 days of last dose date of the lead-in study, or the last non-missing assessment made before the first dose of the study intervention in this study if participants enroll into LIN-MD-66 after 28 days of the last dose date of the lead-in study.

7.2 Medical History

Medical and surgical history data will be coded using Medical Dictionary for Regulatory Activities (MedDRA). The actual version of the MedDRA coding dictionary will be noted in the statistical tables and clinical study report.

Medical and surgical histories in each SOC and preferred term will be summarized by study intervention group using the safety population, for overall and for each age group (6 to 11 years and 12 to 18 years in FC; 7 to 11 years and 12 to 18 years in IBS-C) separately for FC and IBS-C participants. Medical and surgical histories include medical condition prior to Day 1 visit (Visit 2), whether ongoing or resolved.

7.3 Prior and Concomitant Medications

The medication data will be coded using the World Health Organization (WHO) Drug Dictionary, version Global B3 March 2020 or newer. Prior medication is defined as any medication taken prior to the start of study intervention regardless of stop date of the medication. Concomitant medication is defined as any medication taken after the start of study intervention regardless of the start date of the medication. Any prior medications stopped more than 30 days before the date of the first dose of study intervention and any concomitant medications started after the date of the last dose of study intervention will not be presented in the summary tables but will be included in the participant data listings.

Prior and concomitant medications will be coded using the Anatomical Therapeutic Chemical code (4th level, or most specific level available if 4th level is unavailable).

The number and percentage of participants reporting prior or concomitant medications will be summarized, for overall and for each age group (6 to 11 years and 12 to 18 years in FC; 7 to 11 years and 12 to 18 years in IBS-C) by study intervention group, ATC class and code, and preferred drug name using the safety population separately for FC and IBS-C participants. If more than one medication is coded to the same preferred drug name for the same participant, the participant will be counted only once for that preferred drug name.

